7.2.2 Mitigation Plan for Specific Adverse Events

7.2.2.1 Elevated Liver Parameters

All possibly IMP related events of elevated liver parameters must be managed as shown in Table 7-1 (except for DLTs that lead to permanent discontinuation of IMP).

Note: In case of a drug-related \geq grade 2 elevation of ALT and/or AST, pre-medication with dexamethasone must be administered to the patient upon subsequent dosings (see Section 6.4.1).

Table 7-1 Handling of Adverse Events Involving Elevated Liver Parameters

Baseline	Transaminases ^a		Bilirubin ^a	Action with IMP
G0-G1	G2: >3.0 - 5.0 x ULN	or	G2: >1.5 - 3.0 x ULN	Delay dosing ^{b, c}
G0-G1	G3: >5.0 - 20.0 x ULN	or	G3: >3.0 - 10.0 x ULN	Delay dosing ^{d, e}
G0-G1	G4: >20.0 x ULN	or	G4: >10.0 x ULN	Stop dosing
G0-G1	≥G2: >3.0 x ULN	and	>2.0 x ULN	Stop dosing ^f

Abbreviations: ALT = alanine aminotransferase, AST = aspartate aminotransferase, G = grade, ULN = upper limit of normal.

a Any AST, ALT, and / or bilirubin \geq grade 2 elevation needs to be checked 2x/week for up to 4 weeks.

b Re-start at same dose level at 1st occurrence when resolved to \leq grade 1 within 7 days / re-start at a reduced dose level at 2nd occurrence when resolved to \leq grade 1 within 7 days.

c Stop dosing at 3rd occurrence in case of unfavorable benefit-risk assessment by the DMC.

d Re-start at a reduced dose level, but only when resolved to \leq grade 1 within 7 days.

e Stop dosing at 2nd occurrence.

f Patients with ALT/AST>3.0 x ULN and bilirubin >2.0 x ULN with no signs of cholestasis, and for which the cause is at least possibly linked to study drug (i.e. a Hy's law case), must permanently discontinue trial drug.

- If a patient experiences AST, ALT or bilirubin elevations by more than one grade from baseline (grade 0→grade 2 as defined in the NCI-CTCAE Version 4.03), next dose of GEN1029 must be delayed until resolution to ≤ grade 1. Upon resolution to ≤ grade 1 within 7 days, treatment with GEN1029 may be re-started at same dose level for patients with 1st occurrence but at a reduced dose level (DL-1) for patients with 2nd occurrence. If requested by the investigator, the DMC and the sponsor may allow a patient with a favorable benefit-risk assessment to continue in the trial on a reduced dose even if the resolution to grade 1 occurs within 4 weeks. In case of 3rd occurrence a benefit-risk assessment GEN1029 therapy should be permanently discontinued.
- If a patient experiences grade 3 AST, ALT or bilirubin elevations, GEN1029 therapy must be delayed until resolution to ≤ grade 1. Upon resolution to ≤ grade 1 within 7 days treatment with GEN1029 may be re-started at reduced dose level (DL-1). If requested by the investigator, the DMC and the sponsor may allow a patient with a favorable benefitrisk assessment to continue in the trial on a reduced dose even if the resolution to grade 1

occurs within 4 weeks. In case of 2nd occurrence GEN1029 therapy should be permanently discontinued.

- Patients with grade 4 AST (>20.0 x ULN), grade 4 ALT (>20.0 x ULN) and / or grade 4 bilirubin (>10.0 x ULN) elevations, or other grade 4 liver toxicity must permanently discontinue trial drug.
- Patients with ALT/AST >3.0 x ULN and bilirubin >2.0 x ULN with no signs of cholestasis, and for which the cause is at least possibly linked to study drug (i.e. a Hy's law case), must permanently discontinue trial drug.

Please note:

• In case of elevated liver parameters ≥ grade 2, AST, ALT, and bilirubin laboratory values must be checked (unscheduled visits) twice a week for up to 4 weeks until a repeated value below grade 2 is reported.

On-treatment levels	Supportive Care
Transaminases $> 3 - 5 \times ULN$ or bilirubin $> 1.5 - 3 \times ULN$	Consider administering corticosteroids (initial dose of 0.5-1 mg/kg prednisone or equivalent) followed by taper.
Transaminases >5.0 x ULN or bilirubin >3.0 x ULN	Consider administering corticosteroids (initial dose of 1-2 mg/kg prednisone or equivalent) followed by taper.

Table 7-2 Guidance for Supportive Care in Case of Elevated Liver Parameters

7.2.2.2 Infusion-Related Reactions

- Pre-medication to prevent infusion-related reactions may be administered at the investigator's discretion according to local guidelines (e.g., antihistamine, acetaminophen/paracetamol and corticosteroids). The use of paracetamol (acetaminophen) as pre-medication should be considered to be omitted to prevent transaminase elevations, and used with caution during all treatment cycles.
- Grade 1: If an infusion-related reaction grade 1 occurs, the infusion does not need to be interrupted and can be continued at the investigator's discretion at half the infusion rate under close medical supervision.
- Grade 2-3: If an infusion-related reaction grade 2 or 3 occurs, the infusion should be interrupted and appropriate medical management instituted. The infusion may be re-started at the investigator's discretion at half the infusion rate under close medical supervision if symptoms have resolved to ≤ grade 1 within an hour.
 - Patients who have experienced prior infusion related grade 2 or 3 reactions in the trial should be pre-medicated (antihistamine, acetaminophen and corticosteroids are recommended).
 - If the patient has a second Grade 3 infusion-related reaction despite pre-medication, the infusion should be stopped and the patient should be withdrawn from treatment.
- Grade 4: If anaphylaxis or grade 4 infusion-related reactions occur, administration of IMP should be discontinued immediately and permanently and appropriate medical therapy should be administered.

Please note:

- As a routine precaution, patients enrolled in this trial must be observed for 2 hours after each infusion, in an area with resuscitation equipment and emergency agents.
- At all times during GEN1029 infusion, immediate emergency treatment of an anaphylactic reaction according to institutional standards must be assured. In order to treat possible anaphylactic reactions, for instance, dexamethasone 10 mg and epinephrine in a 1:1000 dilution or equivalents should always be available along with equipment for assisted ventilation.
- All pre-medication must be reported on the concomitant medication page in the eCRF

7.2.2.3 Diarrhea

Due to the observation that diarrhea may be associated with GEN1029 treatment in a dose independent manner and can be severe, the following guidance is introduced to manage diarrhea events as they occur (Table 7-3).

Toxicity Grade	Dose Modification	Investigations	Management
Grade 1	Continue treatment	No specific diagnostic work-up recommended. The investigations described below may be considered if the event is prolonged or progressive.	 Close monitoring and consider the following treatments if needed: Loperamide or diphenoxylate/atropine Fluid and electrolyte supplementation
Grade 2	Hold treatment until event improves to $\leq G1$	Blood work-up (including complete blood count, electrolytes, urea, creatinine and C-reactive protein)	Close monitoring and administration of corticosteroids.
Grade 3	Hold treatment until event improves to $\leq G1$	Stool evaluation to rule out infectious etiology (e.g. stool culture and tests for Clostridium difficile toxin, parasite, CMV or other viral etiology, ova and parasite)	For G2, unless diarrhoea is transient, treat with 3 mg oral budesonide once daily. Budesonide may be increased to 6
Grade 4	discontinue treatment	Stool calprotectin and lactoferrin to assess intestinal inflammation Consider CT scan of abdomen/pelvis GI consultation for further evaluation (i.e. capsule endoscopy, colonoscopy or flexible sigmoidoscopy \pm esophagogastroduodenoscopy with biopsy from stomach, duodenum, terminal ileum, colon)	response in 2-3 days. Consider if in-patient care is required for G3/G4 diarrhoea. For G3, treat with 3-6 mg oral budesonide once daily. May administer IV methylprednisolone (2mg/kg/day) if symptoms persist
		NB - Treatment for the event can be initiated while awaiting test results	For G4, administer IV methylprednisolone (2mg/kg/day)*. Corticosteroids should be continued until the event improves to ≤ G1 and then tapered.

Table 7-3 Guidance for Managing Diarrhea

*Patients who respond to IV methylprednisolone can be switched to oral budesonide for continued treatment and taper.

Patients should be made aware of the potential for diarrhoea to occur and to inform the investigator immediately if they experience changes in bowel habits, nausea, vomiting, abdominal pain, cramping, fever and blood or mucus in the stool.

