7.1 Dose-limiting Toxicity

For the purpose of dose escalation, SAEs, non-serious (NS) \geq grade 3 AEs and clinically significant abnormal lab values will be collected and assessed by the DMC for DLTs (in each cohort during the first two cycles; i.e. DLT period of 28 days). National Cancer Institute (NCI) Common Terminology Criteria for Adverse Events (CTCAE) v.4.03 will be used to grade the intensity of adverse events.

DLT criteria are defined below:

Hematological

- Grade 4 neutropenia (i.e., ANC $< 0.5 \times 10^9$ cells/L) for minimal duration of seven days.
- Grade 3 and 4 febrile neutropenia (i.e., $ANC < 1.0 \times 10^9$ cells/L with a single temperature of > 38.3°C or a sustained temperature of ≥ 38°C for more than one hour).
- Grade 4 thrombocytopenia ($\leq 25.0 \times 10^9$ platelets/L) for minimal duration of seven days.
- \geq Grade 3 thrombocytopenia associated with bleeding.
- Grade 4 anemia.

Note: Any grade 4 hematological AE should be checked 2x/ week for up to 4 weeks until a repeated value below grade 2 is reported.

Non-hematological

- Grade 4 infusion-related reactions.
- Grade 4 anaphylaxis.
- Grade 3 infusion-related reactions that do not resolve to \leq grade 1 within 24 hours.
- At least possibly related grade 4 AST, ALT or bilirubin elevations.
- At least possibly related grade 3 AST, ALT or bilirubin elevations that do not resolve to \leq grade 1 within 7 days.
- At least possibly related AST, ALT or bilirubin elevations by more than one grade from baseline (e.g. grade 0→grade 2 as defined in the NCI-CTCAE Version 4.03) that do not resolve to ≤ grade 1 within 7 days.
- At least possibly related \geq grade 2 AST or ALT elevations with concomitant bilirubin >2.0×ULN with no signs of cholestasis, i.e. a Hy's law case.
- Re-occurring of at least possibly related AST, ALT or bilirubin elevations ≥ grade 3, observed in cycle 1 and again in cycle 2 independent of resolution.
- At least possibly related ≥ grade 3 amylase and/or lipase elevations with significant clinical symptoms that do not resolve to ≤ grade 1 or baseline within 7 days.
- Grade \geq 3 diarrhea that does not respond to optimal antidiarrheal treatment within 2 days
- Grade \geq 3 vomiting that does not respond to optimal antiemetic treatment within 2 days
- Grade 3 nausea that does not respond to optimal antiemetic treatment within 7 days

- Any ≥ grade 3 at least possibly related non-hematological AE, which occurs during the first two cycles *excluding*:

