 - \circ Non-hematological laboratory abnormalities that have no clinical consequences and resolve to \leq grade 1 or baseline within 7 days (this also includes electrolyte abnormalities that respond to medical intervention).
 - Grade 3 fatigue persisting for less than 72 hours (optimal medical management must be applied).

Dose-escalation part of the trial:

- Patients experiencing a DLT (an AE fulfilling the DLT criteria within the DLT period of 28 days) must discontinue trial drug immediately.
- Meetings with the DMC will follow after completion of each cohort. Safety data for the specific cohort as well as cumulative safety data for all cohorts (SAEs, NS AEs, laboratory data and DLTs where applicable) will be evaluated.

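### For grade 3 diarrhea Table 7-3 gives only a hold, while 7.1 and 7.3 require trial drug to stop if the event is a DLT, and no passage says which governs

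*Protocol*

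**What the plan says.** **Table 7-3 (protocol 7.2.2.3).** The section presents the table as the way to manage diarrhea whenever it arises and does not limit it to one trial part or period. The dose action for grade 3 is the same as for grade 2: "Hold treatment until event improves to" grade 1 or lower. Only the grade 4 row tells the site to discontinue. The management column foresees grade 3 diarrhea that does not settle ("May administer IV methylprednisolone (2mg/kg/day) if symptoms persist"), but the dose action remains a hold.

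**DLT criteria (protocol 7.1).** Two entries can capture the same event. One is specific: grade 3 or higher "diarrhea that does not respond to optimal antidiarrheal treatment within 2 days". The other is a catch-all for any grade 3 or higher "at least possibly related non-hematological AE, which occurs during the first two cycles". Its exclusions are certain laboratory abnormalities and short-lived grade 3 fatigue; diarrhea is not among them.

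**Consequence of a DLT.** Section 7.1 states for dose escalation: "Patients experiencing a DLT (an AE fulfilling the DLT criteria within the DLT period of 28 days) must discontinue trial drug immediately". Section 7.3 lists a DLT in that period among the conditions under which treatment should be discontinued, and section 8.1 withdraws patients from treatment under the 7.3 rules.

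**After the DLT period and in expansion.** Section 7.2.1.1 allows a first grade 3 event that meets the DLT criteria to be handled by a delay of up to 14 days after discussion with the sponsor. It has further rules for recurrence and names only liver parameters as having rules of their own.

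**Liver section (protocol 7.2.2.1).** Its table applies "except for DLTs that lead to permanent discontinuation of IMP". Section 7.2.2.3 has no such clause.

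**The concern.** A site treating a patient with grade 3 diarrhea in the first 28 days of escalation can open two parts of section 7 and find two different dose actions. The table written for diarrhea says to wait for improvement. The DLT rule says to stop. The table reserves discontinuation for grade 4, and the neighbouring liver section shows that the authors knew how to write a DLT exception, so a reader could take its absence here as deliberate.

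What is at stake is patient safety and consistency between sites. A site that follows the grade 3 row could give a further dose to a patient whom 7.1 says must stop, while another site following 7.1 would withdraw the same patient.

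**Working it through.** No arithmetic underlies the plan's text on this point, so the check sets the passages side by side.

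| Situation of the grade 3 diarrhea | Table 7-3 | 7.1, 7.2.1.1, 7.3 | Compatible? |
|---|---|---|---|
| Escalation, days 1-28, meets a DLT criterion | Hold until grade 1 or lower | Discontinue (7.1, 7.3) | No |
| Escalation, days 1-28, meets no DLT criterion | Hold until grade 1 or lower | No stop required on DLT grounds | Yes |
| Escalation after day 28, or expansion, meets the DLT criteria, first occurrence | Hold until grade 1 or lower | Delay up to 14 days, sponsor discussion (7.2.1.1); longer delay for possibly related toxicity is a stopping rule (7.3) | Yes, but the table does not point to these conditions |

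Grade 4 raises no such conflict: the table and 7.2.1.1 both lead to discontinuation.

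**Can the first row arise in practice?** Section 1.1 sets a 14-day cycle and a 28-day DLT period, so the second dose falls nominally on day 1 + 14 = day 15, inside the window. Suppose grade 3 diarrhea begins on day 4, has not responded by day 4 + 2 = day 6, and is down to grade 1 by day 14. Under Table 7-3 the hold has ended before day 15. Under 7.1 the event became a DLT on day 6 and drug should already have stopped.

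**How wide is the first row?** Under the diarrhea-specific criterion it covers only events that fail 2 days of optimal treatment. Under the catch-all, read literally, it covers every at least possibly related grade 3 diarrhea in the first two cycles, including one that responds within 2 days. The protocol does not say whether the specific entry is meant to displace the catch-all, so the width of the overlap is itself open.

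**Is precedence stated anywhere?** Section 7.2.1.1 says where specific rules apply, but it names only liver parameters and covers only events after the DLT period or in expansion. Sections 7.1, 7.2.2.3, 7.3 and 8.1 do not rank Table 7-3 against the DLT rule.

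**The case against.** The strongest reply is that precedence can be inferred. Section 7.1 uses mandatory language, 8.1 withdraws patients under the 7.3 stopping rules without exception, Table 7-3 is titled as guidance, and section 2.3 describes the diarrhea plan as a guide to diagnostic steps and treatment. The two actions may also be sequential: hold at onset, then stop once 2 days of treatment have failed. The liver section needed a carve-out because its table is mandatory, and the infusion-reaction section has none either.

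Much of this is plausible, and a careful site might act that way. It does not close the gap. The title settles little, since 7.2.1 is also headed as guidance yet contains mandatory stops. The sequential reading works for the 2-day criterion, but the table contains no hand-off: its hold runs until improvement, even when symptoms persist. Under the catch-all there is no 2-day wait. It is fair that the table gives no restart dose, so re-dosing is inferred from the word hold rather than written.

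Four stronger readings are tempting but not supported:

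- **That the conflict changes the mBOIN DLT count.** The DMC assesses DLTs against 7.1. Whether a site held or stopped drug does not alter that classification.
- **That the 2-day DLT clock clashes with a 2-3-day step-up in Table 7-3.** That text sits in a cell broken in extraction and appears to belong to the grade 2 instructions. The DLT criterion starts at grade 3.
- **That the protocol sets no limit on the hold.** The table gives none, but 7.2.1.1 and 7.3 cap delays at 14 days; 7.2.1.1 allows the medical monitor to approve longer, an allowance 7.3 does not repeat.
- **That more than 40% of patients are affected.** The figure in section 10.3.2 is for diarrhea of any grade.

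**Conclusion.** The point holds for grade 3 diarrhea that meets a DLT criterion during the 28-day DLT period of dose escalation. There, Table 7-3 says hold and 7.1 and 7.3 say discontinue, with no stated order between them. The word immediately is 7.1's; 7.3 says treatment should be discontinued. Outside that window the passages are compatible, and the defect is only a missing cross-reference.

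The number of patients affected cannot be given, because the documents report no rate of grade 3 diarrhea, responding or not, within 28 days. The SAP (section 3) states that the expansion part was not started, so the practical reach is the escalation part.

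The conclusion assumes that the grade 3 dose-modification cell of Table 7-3 is complete as extracted. It reads as complete, although other cells in the table have lost words. This is a wording inconsistency that should be corrected because it bears on who is dosed again. It is not a flaw in the dose-finding design.

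**What to change.** Reconcile Table 7-3 with sections 7.1, 7.2.1.1 and 7.3. State in 7.2.2.3 which passage governs a diarrhea event that meets the DLT criteria, first within the DLT period and then after it or in expansion. If the sponsor intends the same arrangement as for liver parameters, the exception already written in 7.2.2.1 is a model. For the later period, a cross-reference to the delay and recurrence rules of 7.2.1.1 and the stopping rules of 7.3 would be enough. Which clinical rule should apply is for the sponsor and the DMC to decide.

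The cost is an alignment of protocol wording. No assessment, sample size or analysis changes.

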7.3 Safety Stopping Rules

Treatment with IMP should be discontinued due to safety concerns under the following conditions:

• Patients experiencing a DLT (an adverse event fulfilling DLT criteria within the DLT period during the dose-escalation part of the trial).

- If the patient experiences an adverse event fulfilling the DLT criteria after the DLT period has ended in the dose-escalation part of the trial or during the expansion part of the trial, that fails to resolve to ≤ grade 1 or baseline within 14 days after the planned dosing date. N.B. Grade 4 AEs fulfilling DLT criteria will always lead to IMP discontinuation.
- If more than two dose reductions are required.
- Dose delay of more than 14 days due to toxicity possibly related to GEN1029.
- Possibly related event of elevated liver parameters
 - Patients with grade 4 AST (>20.0 x ULN), grade 4 ALT (>20.0 x ULN) and / or grade 4 bilirubin (>10.0 x ULN) elevations, or other grade 4 liver toxicity.
 - 2nd occurrence of a grade 3 AST, ALT or bilirubin elevation (if first occurrence resolved to \leq grade 1 within 7 days).
 - Patients with ALT/AST>3.0 x ULN bilirubin >2.0 x ULN with no signs of cholestasis, and for which the cause is at least possibly linked to study drug (i.e. a Hy's law case).
 - In case of a negative benefit-risk assessment performed by DMC due to 3rd occurrence of AST, ALT or bilirubin elevations by more than one grade from baseline (grade 0→grade 2; if it resolved to grade 0 at prior occurrences).
- 2nd occurrence of a grade 3 infusion-related reaction despite pre-medication prior to infusion.
- 1st occurrence of anaphylaxis or grade 4 infusion-related reactions.

Please note:

• Observation procedures and assessments are to be continued for the rest of the cycle. Patients should, whenever possible, irrespective of the reason for discontinuation, be examined as soon as possible (specified as the end of treatment visit).
8 DISCONTINUATION, FOLLOW UP AND COMPLETION

8.1 Discontinuation of Treatment

Patients will be withdrawn from treatment for the following reasons:

- Safety Stopping Rules (as defined in Section 7.3)
- Pregnancy
- Patient choice
- Investigator or sponsor decision due to individual patient safety issues not covered by other withdrawal criteria
- Disease progression
- Initiation of other anti-cancer treatment (the expansion part only)
- Intercurrent illness that precludes further participation or requires a prohibited concomitant treatment

Patients should, whenever possible, irrespective of the reason for discontinuation, be examined as soon as possible at the end of treatment visit.

8.2 Withdrawal from the Trial

Patients will be withdrawn from the trial (dose escalation or expansion parts), including safety follow-up evaluations and follow-up contact, for the following reasons:

- A patient may withdraw from the trial at any time at his or her own request
- At the discretion of the investigator for safety, behavioral, compliance, or administrative reasons
- Lost to Follow-Up (see Section 8.4)
- Patient died
- Trial closure
- Initiation of other anti-cancer treatment (the dose-escalation part only)

If the patient withdraws consent for disclosure of future information, the sponsor may retain and continue to use any data collected before such a withdrawal of consent.

If a patient withdraws from the trial, he or she may request destruction of any samples taken and not tested, and the investigator must document this in the site trial records.

The sponsor will make any effort to ensure patients are followed up for completion of safety assessment in the trial. See Table 1-1 and Table 1-6 for data to be collected at the time of trial discontinuation and follow-up and for any further evaluations that need to be completed.

When a patient withdraws before completing the trial, the reason for withdrawal is to be documented in the eCRF and in the source document. Trial drug assigned to the withdrawn patient may not be assigned to another patient.

Patients who withdraw will not necessarily be replaced.

Withdrawal From the Use of Samples in Future Research

The patient may withdraw consent for use of samples for research (refer to Section 13.2.5). In this case, samples will be destroyed after they are no longer needed for the clinical trial. Details of the sample retention for research are presented in the ICF.

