8.3 Safety Follow up Evaluations

Patients discontinuing from treatment for any reason will have safety follow-up visits 30 and 70 days after last treatment and will also be contacted every 13 weeks after last dose until end of trial.

Data collected should be added to the adverse events eCRF and the concomitant medications eCRF.

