9.1.4 Concomitant Medication

Any medication or therapy other than GEN1029 is considered concomitant medication and should be recorded in the eCRF with the following information:

- Start date
- Route of administration
- Stop date of administration or ongoing at trial termination
- Indication/reason for use
- The total daily dose should be filled in whenever possible.

Relevant prior concomitant medication given within 4 weeks prior to screening and all medication given from visit 0 (Screening) until the 70-day safety follow-up must be recorded.

During the patient follow-up period only new anti-cancer treatment will be collected.

9.1.5 **Prior Cancer Therapy and Surgery**

Administration of prior anti-cancer therapies and surgeries must be reported in the appropriate section of the eCRF. Number of cycles, best response and stop reason along with dates of administration and progression should be reported.

Radiotherapy should be recorded if the indication is cancer.

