#### 4.1 Trial Period and Visit Window Definitions

#### 4.1.1 Trial Periods

Screening period will be defined as the period between signature of the ICF and the date of first IMP administration.

On-Treatment period will be defined as the period between first IMP administration (included) and last IMP administration, including the safety follow-up period (taking the maximum of date of last IMP +70 days, end of treatment visit and safety FU visit).

Follow-up period will be defined as the period after the On-Treatment period (that includes the safety FU period) +1 day until the date of last contact.

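### Protocol 8.2 ends follow-up when an escalation patient starts other anti-cancer treatment, in conflict with 8.3 and Table 1-1, so new events up to day 70 and later deaths are not actively collected

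*Protocol*

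**What the plan says.** - **Protocol 8.2** opens its list with "Patients will be withdrawn from the trial (dose escalation or expansion parts), including safety follow-up evaluations and follow-up contact". The last reason on the list is "Initiation of other anti-cancer treatment (the dose-escalation part only".
- **Protocol 8.1** has the mirror entry among reasons for stopping treatment: "Initiation of other anti-cancer treatment (the expansion part only". In the expansion part, the same event therefore stops treatment without ending follow-up. No reason is given for the difference.
- **Protocol 8.3**: "Patients discontinuing from treatment for any reason will have safety follow-up visits 30 and 70 days after last treatment". It adds contact every 13 weeks after the last dose and makes no exception by trial part.
- **Protocol 9.1.4**: "During the patient follow-up period only new anti-cancer treatment will be collected".
- **Table 1-1 (escalation)**: footnote 2 makes a new anti-cancer treatment a trigger for the end-of-treatment visit. Footnote 19 has new anticancer treatments recorded in the 30-day, 70-day and 13- to 52-week columns. Footnote 21 moves the safety visit to the date of withdrawal if that falls before day 70, unless one took place in the previous 14 days.
- **Protocol 10.2** ends AE and SAE reporting at the 70-day visit or the withdrawal visit, whichever is earlier.
- **SAP 4.1.1** sets the end of the on-treatment period by "taking the maximum of date of last IMP +70 days, end of treatment visit and safety FU visit". SAP 17.3 builds the treatment-emergent AE tables on that period. SAP 15.8 analyses overall survival in the full analysis set and censors at the last date known alive.

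**The concern.** A patient who stops GEN1029 for progression and starts another therapy before day 70 falls under both 8.2 and 8.3, and the two give opposite instructions. If sites follow 8.2, active detection of adverse events ends when the new therapy starts, and so do the contacts at which a death would be learned of. The safety profile is a primary objective of the escalation part. The SAP covers that part alone, because the expansion was never opened, so the rule applies to all 48 subjects. A reader of the report could not tell an absent event from absent observation.

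**Working it through.** The plan states no figure on this point. The check sets the rules side by side for one patient and then does simple day arithmetic.

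**1. The patient.** An escalation patient stops for progression and starts other therapy on day *t* after the last dose, with *t* below 70.
- Under 8.2 the patient leaves the trial and follow-up ends.
- Under 8.3 the 30- and 70-day visits and the 13-weekly contacts go ahead.
- Footnote 2 handles the event as end of treatment. Footnote 19 presumes contacts at which new anticancer treatments are recorded. SAP section 12 tabulates subsequent therapies from such data.
- Under 10.2, if 8.2 is followed, AE and SAE reporting closes at the withdrawal visit.

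**2. What survives withdrawal.** The footnote 21 visit remains. Sections 10.2 and 10.6 keep following SAEs and related non-serious grade 3 or higher AEs that are still ongoing. Section 10.4.4 keeps IMP-related SAEs reportable after participation ends.

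**3. What is lost.** Three things are no longer actively collected: new-onset events between withdrawal and day 70, the outcome of unresolved lower-grade events, and later deaths. Deaths are SAEs under 10.2.4, and footnote 18 has SAEs collected at the 13- to 52-week contacts, which 8.2 cancels.

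**4. Days lost per patient.** The 70-day window comes from 8.3 and SAP 4.1.1. The value of *t* is an assumption, and withdrawal is taken to occur on day *t*. Share observed = *t*/70; days unobserved = 70 − *t*.

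| *t* (assumed) | Observed | Unobserved days |
|---|---|---|
| 14 | 20% | 56 |
| 28 | 40% | 42 |
| 42 | 60% | 28 |
| 56 | 80% | 14 |

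Table 1-1 allows ±7 days around each visit. A start before day 23 (30 − 7) precedes both scheduled visit windows, and a start before day 63 (70 − 7) precedes the 70-day window.

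**5. Across the trial.** The nominal total is 48 × 70 = 3360 person-days. Let *f* be the share of patients starting therapy before day 70, also an assumption. Lost person-days = *f* × 48 × (70 − *t*).
- *f* = 20%, *t* = 56: 0.2 × 48 × 14 = 134 (4%).
- *f* = 40%, *t* = 28: 0.4 × 48 × 42 = 806 (24%).
- *f* = 60%, *t* = 14: 0.6 × 48 × 56 = 1613 (48%).

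The range is wide because the documents supply neither input.

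**6. Effect on SAP outputs.**
- *Overall survival*: once contact ends, the last date known alive is at or near the start of new therapy. Progressed patients who take no further therapy stay in contact and their deaths are recorded; those who do take it are censored. Censoring then depends on disease course. Its direction cannot be settled from the documents.
- *Time to first AESI*: SAP 17.3 censors event-free subjects at the end of the treatment period. If that means the 4.1.1 period, censoring can fall after last contact. If it means the end date of IMP in SAP 4.6, which is capped at last contact, it cannot. The SAP does not say which.
- *Progression-free survival*: this rule does not change it. SAP 15.6 already censors at new therapy.

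**The case against.** The strongest reply is that 8.2 is a later step that overrides 8.3. Death and lost contact are on the same list and must override it. Footnote 21 and 10.2 fit that reading, because both provide for withdrawal before day 70. The split by part may even be deliberate, since Protocol 11.4.5.1.3 analyses survival only in the expansion part. This deserves weight, but the documents do not state such a hierarchy, and footnotes 2 and 19 point the other way for this particular event. The objectives table lists overall survival for the escalation part, and SAP 15.8 analyses it. Section 8.2 also says "The sponsor will make any effort to ensure patients are followed up for completion of safety assessment in the trial", but that sets no visit and no window.

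Four stronger readings might be inferred, and the documents do not support them:
- **That all safety follow-up, or everything except spontaneous reports of related SAEs, is lost.** The footnote 21 visit and the continued follow-up under 10.2 and 10.6 remain. Footnote 26 also asks for repeat liver tests for grade 2 or higher elevations.
- **That the treatment-emergent AE percentages are miscalculated because the SAP assumes 70 days.** They are crude proportions of subjects. Ending the window at last contact would leave them unchanged; the shortfall lies in what is collected.
- **That the typical escalation patient is affected.** Inclusion criterion 2 requires that no standard therapy likely to help is available, or that the patient is not a candidate for it. That argues against assuming frequent early switching.
- **That recording new therapy becomes impossible.** A therapy begun between contacts can be discovered at the next one. In that case observation runs longer than the table above assumes.

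**Conclusion.** The conflict between 8.2 and 8.3, and with footnotes 2 and 19 of Table 1-1, is in the current text. If 8.2 is followed, new-onset AEs up to day 70, unresolved lower-grade AEs and later deaths are under-ascertained in the only part of the trial that was run, and survival censoring is likely informative. For an affected patient the loss is 14 to 56 of 70 days if therapy starts 56 to 14 days after the last dose and withdrawal takes effect that day. The number of affected patients is unknown, so no size of bias in the safety results can be claimed. The DLT endpoint on days 1 to 28 is not shown to be affected.

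**What to change.** **Protocol.** Reconcile 8.1, 8.2, 8.3, 10.2 and Table 1-1 so that starting other anti-cancer treatment in the escalation part does not cancel the safety visits and survival contacts already scheduled. The 8.2 bullet and the expansion-only limit in 8.1 must change together. Removing the 8.2 bullet alone would leave the escalation part with no entry for this event in either list, while footnote 2 already handles it as end of treatment. How treatment itself is handled is for the sponsor to state consistently; the point here is data collection. Flag AEs with onset after new therapy in the listings.

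**SAP.** Report by dose level how many subjects were observed for less than 70 days after the last dose because of new therapy. State that the time-to-first-AESI curves are censored no later than last contact.

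**Cost.** A few sentences in each document. The visits and contacts are already in the schedule, and the SAP items need only dates already recorded. AEs after new therapy are confounded by it, which the flag makes visible. Where follow-up is already over, the protocol change recovers little, and the SAP items are what remain useful.
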